1.0 Introduction – Background and Rationale

Background

The emergence of dissemination and implementation (D&I) science has driven a rapid increase in studies of how new scientific discoveries are translated and developed into evidence-based programs and policies. However, D&I science has paid much less attention to what happens to programs once they have been implemented. Public health programs can only deliver benefits if they reach maturity and sustain activities over time. In order to achieve the full benefit of significant investment in public health research and program development, we need to understand the factors related to sustainability and develop tools and trainings that support strategic long-term program sustainability. The goal of this proposed study is to increase the capacity for sustainability among evidence-based tobacco control (TC) programs.

Rationale

Sustainability as an important next step in dissemination and implementation (D&I) research.

Demonstrating that an intervention is effectively implemented, (the initial process of embedding interventions within settings¹²), is only the first step in impacting the health and wellness of a target population. In order for the population to reap the benefits of an implemented evidence-based intervention, it must be sustained over time. In recognition of this, several recent D&I papers have called explicitly for sustainability research as an essential next step in the field.^{10,11,13-21} Program sustainability—the extent that interventions can continue to be delivered over time and institutionalized within settings¹²—is a complex process, often fraught with challenges.^{16,21-23} Research consistently indicates that even effectively implemented interventions risk failure when funding ends^{10,20,24} or when planning and training stops.²⁵ In fact, it is estimated that up to 40% of programs fail within two years of losing funding.²⁶ Implementing a program and then failing to sustain it can have disastrous consequences for the community through loss of trust and waste of valuable community resources.²⁷ Though there is growing interest in the study of program sustainability, there is little agreement on how to best sustain initiatives over time.^{23,28} This is due, in large part, to the historical lack of sustainability assessment tools that are both reliable and widely disseminated^{16,29} and an essential absence of an evidence-based action planning process for sustainability.

Importance of sustaining evidence-based TC for public health.

As of 2013, 42.1 million—or 1 in 5—adults in the US smoke, which leads to an estimated 480,000 preventable deaths per year due to tobacco use. Approximately 61,000 of those deaths occur from secondhand smoke exposure. According to the Center for Disease Control and Promotion (CDC), if smoking continues at its current rate, more than 5 million of today's youth will die prematurely, and the economic cost of smoking will rise to more than \$300 billion per year.³⁰

Tobacco use has long been identified as a major preventable cause of death and disease in the US. There is also little debate that TC expenditure directly impacts tobacco use rates in the US. Between 1985 and 2003, US adult smoking prevalence declined from 29.5% to 18.6%. This sharp decline directly correlated with state TC program funding rates.¹ Farrelly et al. estimates, “If, starting in 1995, all states had funded their TC programs at the minimum or optimal levels recommended by the CDC, there would have been 2.2 million to 7.1 million fewer smokers by 2003.”¹ Given the established evidence for the state TC model and the work left to do in this field, it is vital that these programs continue in all 50 states, both to improve quality of life and reduce

the massive healthcare costs incurred by smoking-related illness.¹ Failing to sustain evidence-based TC initiatives will likely lead to stagnation in smoking cessation rates and an increase in new smokers.¹

The need for evidence-based sustainability training and technical assistance. Empirical evidence has established that program sustainability can be improved through training and technical assistance;^{11,31-33} however, to date, no evidence-based program sustainability training curricula exists. Thus, systematic methods are needed to empirically develop, test, and disseminate sustainability training to improve institutionalization of evidence-based programs. While there is a growing body of research on the factors affecting sustainability,^{11,15,20-23,34} virtually no empirical work has been done to translate the components of program sustainability capacity into practical guides and tools for practitioner utilization.^{11,28} Our work with over 50 public health programs indicates that managers, evaluators, and practitioners need assistance in using sustainability assessment results to inform sustainability planning priorities, along with a clear process for completing a written sustainability plan that is easy to implement.

Importance of utilizing an action-oriented approach. Literature indicates that the best practice for impacting long-term behavior and institutional change is a hands-on, action-oriented, in-person³⁵⁻³⁷ training program. A study that involved action planning training with coalition groups working on substance abuse initiatives in Tennessee found positive changes in sustainability readiness (increased infrastructure capacity) post training,¹¹ and a meta-review of health behavior change outcomes found that intervention amount, duration, and penetration all impact level of behavior change.^{38,39}

Research also highlights the importance of creating an action plan to move sustainability progress forward. Creating a sustainability plan has predicted both program survival and post-launch funding,⁴⁰ and obtaining future funding facilitated the institutionalization process of a new intervention.⁴¹ Additionally, plan specificity and attitude toward intervention predicted plan adherence,⁴² and perceived self-efficacy, policy support, and level of institutionalization predicted sustainment of plan initiatives.²⁵

Innovation

This study makes important contributions to D&I science and is innovative because it:

1. *Develops the first ever evidence-based Program Sustainability Action Planning Model and Training Curriculum.* By establishing an evidence-based method for action planning and technical assistance surrounding program sustainability, we are supporting state TC programs and other evidence-based public health initiatives to sustain their positive impact in a tumultuous funding climate. In addition, this work will advance the field of study of action planning and technical assistance in general which can contribute to aspects of the D&I field beyond sustainability.

2. *Links closely with practice at an opportune time.* As part of the DP15-1509, National State-Based TC Program Funding Announcement set forth by the CDC, all 2015 awarded applicants (includes all states and territories) are “required to develop a sustainability plan to ensure sustainability and maintaining a state based TC program” and “provide measures of execution of all activities as outlined in the sustainability plan.”² Our development of the Program Sustainability Action Planning Training and broad dissemination will assist states in fulfilling this requirement and establishing their capacity to continue sustainability planning over time.

3. Further advances D&I science related to establishing validated measures for sustainability. The study will also provide further clarity on the challenges, benchmarks, and programmatic factors that contribute to sustainability (versus implementation) of an intervention. We will also use the data collected to explore the predictive validity of the Program Sustainability Assessment Tool, which will enable programs to better plan for and improve the sustainability of effective programs.

4. Provides broad dissemination of training materials and results. The curriculum and lessons from the training program will be systematically disseminated (at no cost) to several key audiences (e.g., trainers in federal and state agencies, staff in public health agencies). Since our training program focuses on capacity for sustainability, our methods and approaches will be applicable to numerous other public health issues.

1.0 Objectives

The overall goal of this proposed study is to increase the capacity for sustainability among evidence-based tobacco control (TC) programs. Although all 50 states have implemented evidence-based TC programs and policies, states vary in their abilities to support and sustain these programs over time. Most states still do not meet the CDC recommended level for funding their TC program allowing for tobacco use to remain the leading cause of preventable disease and death in the US.¹ Also, as part of the 2015 National State-Based Tobacco Control Program Funding Announcement released by the CDC,² all awarded state applicants are “required to develop a sustainability plan” and “provide measures of execution of all activities as outlined in the sustainability plan”. There are currently no available resources specifically designed to help states meet this requirement making this project imperative for states to effectively meet this important funding requisite.

[figure not shown]
- Phase 1 (Aim 1) focuses on refining and finalizing our evidence-based Program Sustainability Action Planning Model and Training Curriculum and deliver to 12 states. The Program Sustainability Action Planning Training will incorporate experiential learning methods³⁻⁶ and includes: action planning workshops, development of action plans with measurable objectives to foster institutional changes, and technical assistance.
- Phase 2 (Aim 2) will use a randomized effectiveness trial to assess the Program Sustainability Action Planning Training in 24 states (12 intervention, 12 comparison). Evaluation of our training program is centered on the theory of change.^{7,8}
- Phase 3 (Aim 3) focuses on responding to study results by making any needed revisions and conduct widespread dissemination of our Program Sustainability Action Planning Model and Training Curriculum starting with the 12 comparison states.

3.0 Selection of Participants – Eligibility Criteria

Recruitment. A total of 24 state TC programs will be recruited to participate in this study. We believe this number is feasible for three main reasons: (1) this training will be in high demand because of the CDC’s requirement for all state TC programs to complete a sustainability plan; (2) our strong relationships and past success in evaluating state level TC programs; (3) our project consultant’s 20+ years working directly with state level tobacco programs ([name]).

State selection. We will recruit 24 states, and then randomly assign each state into intervention and comparison conditions. To ensure that both the intervention and comparison groups are equally diverse in terms of organizational factors relevant to tobacco control, we will stratify states using the following three criteria: (1) tobacco control policy progress, (2) smoking rates, and (3) funding for TC program. Tobacco control policy progress is operationalized as the American Lung Association's (ALA) 2015 Smoke-free Score for each state.⁸⁸⁻⁹⁰ The ALA "grades" each state annually according to the comprehensiveness of its smoke-free policies (higher scores indicate more comprehensive smoke-free policies). 2013 adult smoking rates are used for smoking rates⁹⁰ and funding is measured as the actual amount spent on tobacco control as a percentage of the CDC-recommended amount of spending for FY2015.^{88,91} Together, these three indicators characterize states' needs (smoking rates), inputs (funding), and environments (policy). States will also be chosen based on willingness to participate and receipt of prior sustainability training. Figure 3 is divided into quadrants by the median smoking rate and median Smoke-free Score. The size of the circles within each quadrant represents the varying levels of funding. The quadrants delineate the primary selection guidelines. Six states from each quadrant representing varying levels of funding will be randomly assigned to either the intervention or comparison group. This process will guard against selecting a disproportionate number of well- or poorly-funded programs for each group. Furthermore, it will ensure both the intervention and comparison groups are evenly varied in terms of needs and policy environments. All participants in this study are aged 18 years or older. States agreeing to participate in the study will learn of their group assignment after completing the PSAT.

Figure 3. Selection criteria for intervention and comparison groups

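### Funding is named as a stratification criterion, but no described step balances it between arms, and Equation 1 does not name baseline funding

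*Combined protocol and SAP*

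**What the plan says.** Section 3.0 (State selection) sets the aim: "To ensure that both the intervention and comparison groups are equally diverse in terms of organizational factors relevant to tobacco control". To reach it, "we will stratify states using the following three criteria: (1) tobacco control policy progress, (2) smoking rates, and (3) funding for TC program". Funding is defined there as FY2015 tobacco control spending relative to the CDC's recommended level, so a pre-randomisation value exists for every state.

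The steps that follow are these. Figure 3 is cut at the median smoking rate and the median smoke-free score, and circle size shows funding. "The quadrants delineate the primary selection guidelines". Then: "Six states from each quadrant representing varying levels of funding will be randomly assigned to either the intervention or comparison group". The order is recruitment first: "We will recruit 24 states, and then randomly assign each state into intervention and comparison conditions". Section 1.0 (Objectives) gives 12 states per arm overall. The split within a quadrant is not stated.

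Two assurances close the paragraph. For funding: "This process will guard against selecting a disproportionate number of well- or poorly-funded programs for each group". For smoking rate and policy: "it will ensure both the intervention and comparison groups are evenly varied in terms of needs and policy environments".

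In Section 9.0, Equation 1 contains baseline PSAT, group, dose, group-by-dose and a covariate vector X_it. The vector is described only by type (programme, organisation, community, funder). Time runs over 1 and 2, and only PSAT is marked as a time-0 value. The text after Hypothesis 1 speaks of measuring change in these covariates. C.6.e plans descriptive statistics by arm at every time point. Funding is among the abstracted variables (Section 10.0), and abstraction takes place at baseline and twice later (Section 5.1).

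**The concern.** The paragraph promises protection on three criteria but describes a mechanism for two. Choosing states of varied funding spreads funding across the 24 states. It does not constrain which of them go to which arm. With 12 states per arm, chance alone can leave one arm noticeably better funded, and the sponsor itself treats funding as relevant to the outcome.

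The analysis does not clearly close the gap. Baseline funding is not named in Equation 1, and if funding enters through X_it as indexed, the value used would be measured after randomisation. Section 1.0 (the action-oriented approach) reports that making a sustainability plan predicted later funding, so follow-up funding might itself respond to the training. At stake are precision, the credibility of a stated safeguard and, in that conditional case, dilution of the effect under test.

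**Working it through.** The plan gives no figure for funding balance, so there is none to reproduce.

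**1. Mechanism, criterion by criterion**

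| Criterion | Forms strata? | Described step acting on the arm split | Assurance given |
|---|---|---|---|
| Smoking rate | Yes, median cut | Randomisation within quadrant | Evenly varied arms |
| Policy score | Yes, median cut | Randomisation within quadrant | Evenly varied arms |
| Funding | No; circle size, and choice of varied states | None | No disproportion in either arm |

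**2. Assumptions.** The documents give no state funding data. I assume 3:3 allocation within each quadrant and 12 well-funded states among the 24. X is the number of well-funded states in the intervention arm; an 8-4 or worse split is |X − 6| ≥ 2.

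**3. Quadrants only, three well-funded states in each.** Per quadrant, the number in the intervention arm is 0, 1, 2 or 3 with probabilities 1/20, 9/20, 9/20, 1/20. Convolving four quadrants gives P(X = 8, 9, 10, 11) = 0.0994, 0.0243, 0.0033, 0.0002. The sum is 0.1272; doubled, 25.4%. For 9-3 or worse the figure is 5.6%.

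**4. No stratification.** Hypergeometric (24 states, 12 well-funded, 12 drawn): 22.0% for 8-4 or worse, 3.9% for 9-3 or worse. If funding is unrelated to quadrant, the quadrants therefore give no protection on it.

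**5. Adjacent pairs by funding rank within quadrant.** With three well-funded states per quadrant, only the middle pair is discordant, so X = 4 + Binomial(4, ½). P(X = 4 or 8) = 2/16 = 12.5%; 9-3 cannot occur.

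**6. Other spreads of the 12 well-funded states (8-4 or worse)**

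| Well-funded per quadrant | Quadrants only | Paired |
|---|---|---|
| 3,3,3,3 | 25.4% | 12.5% |
| 4,3,3,2 | 24.1% | 0 |
| 4,4,2,2 | 22.7% | 0 |
| 5,3,3,1 | 19.6% | 12.5% |
| 5,4,2,1 | 18.0% | 0 |
| 5,5,1,1 | 12.5% | 12.5% |

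**7. Continuous funding.** For normal funding unrelated to quadrant, the arm difference has SD √(2/12) = 0.41 funding SD with quadrants only and, by simulation, 0.21 with pairing. The chance of a difference above 0.5 SD falls from about 22-23% to about 2%; with right-skewed funding, from 24% to 3%. If quadrant explains 25% or 50% of funding variance, the quadrant-only figure is already about 16% or 8%.

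**8. Effect on the arm comparison.** If well- and poorly-funded states differ by 0.5 to 1.0 SD on the outcome (assumed), an 8-4 split shifts the unadjusted difference by (8/12 − 4/12) × 0.5 to 1.0 = 0.17 to 0.33 outcome SD, before any adjustment for baseline PSAT.

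**9. Equation 1.** Baseline PSAT is the only term fixed at time 0. X_it is not enumerated, so the documents do not settle whether funding enters or at which time. A follow-up value would not correct a baseline imbalance and could lie on the path from training to outcome.

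**The case against.** Four points on the other side carry weight.

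- Randomisation balances funding in expectation. A reader might infer that the comparison is biased by design; the documents do not support that. Baseline PSAT, which has a Funding Stability domain, may absorb part of any imbalance, and leaving quadrant out of the model errs on the conservative side.
- The closing assurance on funding is worded more softly than the one on needs and policy, and Figure 3 is not available, so funding classes in it cannot be excluded. But the opening aim covers all three criteria, and the text that describes the figure gives no funding cut.
- A reader might infer that Equation 1 prescribes follow-up funding and so removes part of the training effect. That over-reads a subscript. The notation is loose (group is indexed by state in one term and by state and time in another), a constant baseline covariate can sit in X_it, and funding is also abstracted at baseline. The pathway may be weak as well: the CDC requires every awarded state to develop a plan, so plan creation need not differ by arm. The point stands only as a conditional one.
- A reader might set the shift in step 8 against the planned effect size of 1.25. That is not valid: 1.25 is in SDs of PSAT change (Section 9.0, C.6.d), while the shift is in SDs of an unspecified outcome.

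**Conclusion.** The stated safeguard on funding has no described mechanism. The consequence is a risk of chance imbalance and lost precision. Under the assumed 3:3 split and three well-funded states per quadrant, about one allocation in four would be 8-4 or worse, no better than without stratification; pairing halves that and rules out 9-3. The gain shrinks if quadrant predicts funding, and pairing does not lower the 8-4 risk in the 5,5,1,1 case. How much of the training effect adjustment for follow-up funding could absorb cannot be quantified from the documents. Severity is minor to moderate: the defect is clear in the text, its size rests on assumed inputs, and the remedy is cheap.

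**What to change.** **If states are not yet randomised:** rank the six states in each quadrant by FY2015 funding percentage, form three adjacent pairs, and randomise one of each pair to each arm. All 24 states are recruited before assignment, so this is feasible, and it also fixes 3:3 per quadrant and 12:12 overall.

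**In either case:** prespecify baseline FY2015 funding percentage (1 df) as a covariate in the primary model, and state that this value, not follow-up funding, is the adjustment value.

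**If states are already randomised:** describe the funding step that was used or qualify the assurance, and report funding by arm in the baseline descriptives already planned in C.6.e.

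Adding quadrant (3 df more) is optional and sensible only if the other X_it terms are few.

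**Cost.** No new data; the FY2015 values are already needed for Figure 3. Counting states as units, 24 − 5 = 19 df remain after the intercept, baseline PSAT, group, dose and group-by-dose. With zero, five or ten other X_it terms, adding funding moves the one-sided 5% critical t from 1.7291 to 1.7341, 1.7613 to 1.7709, and 1.8331 to 1.8595: rises of 0.3%, 0.5% and 1.4%. A covariate also costs precision through chance correlation with group. The residual variance it must explain to break even is 1 − 1/(SE inflation × t ratio)². With no other terms and quadrants only, this is 1 − 1/(1.026 × 1.003)² ≈ 6%. Simulating with the X_it terms in the model as independent normal covariates gives:

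| Added terms | Assignment | 0 other terms | 5 | 10 |
|---|---|---|---|---|
| Funding (1 df) | Quadrants only | 6% | 7-8% | 12% |
| Funding (1 df) | Paired | 2% | 4% | 9% |
| Funding + quadrant (4 df) | Quadrants only | 9% | 18% | 40% |
| Funding + quadrant (4 df) | Paired | 5% | 15% | 37% |

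The SE inflation behind this table leaves out dose and group-by-dose. Counting them raises the 1-df figures slightly and the 4-df figures more (quadrants only: about 11%, 23% and 48%). Funding alone is the safer minimum.

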4.0 Participant Registration

We will work with the Office on Smoking and Health (OSH) at the CDC to identify a list of state TC program managers to contact during study recruitment/registration. We will contact all identified program managers and invite them to participate in the study, as well as provide project fact sheets, outlining benefits and responsibilities of being a part of the study. Once we divide states into intervention or comparison group, we will work with each state program manager to identify a sustainability workgroup consisting of 5-12 members actively involved in TC initiatives in the state. In our experience, we have found that the desired organizational outcome (institutionalization) is best achieved if an integrated workgroup comprised of internal state health department staff (i.e., the program coordinator and TC program director); external stakeholders (i.e., TC coalition members or national TC advocacy groups); and policy makers (especially if there is a TC champion in the state) complete the PSAT and actively participate throughout the 6-step action planning process. Therefore, the composition of each state program's sustainability workgroup will not be randomized.

Participants receive a consent letter (Appendix D, attached) that details participation in the study. Participants are able to review this letter privately and for several days. To register, participants email the research project manager identified in the letter. Participants are able to ask questions at all times using phone and email contact information for the research team located at Washington University in St. Louis.

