5.1 Treatment Plan

Phase 1 (Aim 1)

Delivery of Program Sustainability Action Planning Training (intervention protocol).

The Program Sustainability Action Planning Training will be designed to assist states in completing each of the 6 steps in the action planning process and consists of three components (1) pre-workshop preparation, (2) an in-person two day workshop, and (3) ongoing technical assistance and support. Each component will be defined by experiential learning and participation by multiple stakeholders. A sustainability workgroup will be defined for each state consisting of 5-12 members who are actively involved in TC initiatives in the state. To ensure training fidelity, delivery of all training components will be overseen by [name], Principal Investigator and [name], Project Manager.

Preparing for the workshop. Approximately two months before scheduled workshop, we will work with the state tobacco control program manager to identify the list of TC stakeholders who will be involved in workgroup based on our standardized workgroup selection criteria.³¹ Once a list is determined, we will work with the program manager to plan a time to conduct an "Introduction to Sustainability" webinar. This webinar educates listeners on the Program Sustainability Framework (8 domains), defines the parameters one should use when completing PSAT items (i.e., define the "program"), explains how to complete the PSAT online, and provides a time for state-specific Q & A. Prior to the webinar, we will ask the program manager and all stakeholders to complete an *optional* Qualtrics survey, assessing general state tobacco control program sustainability perceptions and individual demographics (age, gender, race, per NIH reporting requirements). Personally identifiable information will not be collected. The pre-

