Comparison state programs will participate in the PSAT assessment, record abstraction, and a key informant interview and survey with state program managers at three time points. Before taking the PSAT, we will work with the state tobacco control program manager to identify the list of TC stakeholders who will be involved in workgroup based on our standardized workgroup selection criteria.³¹ Once a list is determined, we will work with the program manager to plan a time to conduct an “Introduction to Sustainability” webinar. This webinar is identical to the webinar issued to the intervention group, because state programs will be informed of their group selection after completing the PSAT. The webinar educates listeners on the Program Sustainability Framework (8 domains), defines the parameters one should use when completing PSAT items (i.e., define the “program”), explains how to complete the PSAT online, and provides a time for state-specific Q & A. Prior to the webinar, we will ask the program manager and all stakeholders to complete an *optional* Qualtrics survey, assessing general state tobacco control program sustainability perceptions and individual demographics (age, gender, race, per NIH reporting requirements). Personally identifiable information will not be collected. The pre-workshop webinar is important for two reasons: (1) it familiarizes all workgroup members with the components of sustainability as outlined in our framework, and (2) introduces the PSAT and steps for completing the PSAT online. The webinar instructs users to answer N/A to PSAT items they are unable to accurately assess. The pre-workshop webinar generally lasts 45 minutes. Comparison states will receive a detailed sustainability assessment report outlining the state’s PSAT scores. There will also be follow-up correspondence, discussing state-level aggregated results of the PSAT, as well as recommendations for action planning next steps. At this point, we will provide a brief packet with resources about program sustainability. However, comparison states will not receive any other component of the training until year four of this project, when they will disseminate the finalized curriculum materials. Some comparison states might independently implement sustainability plans over the course of the grant. We will track implementation and account for it in analyses.

Phase 2 (Aim 2)

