The PSAT has established reliability and face validity for effectively measuring program capacity for sustainability.⁴³ The PSAT contains 40 questions (5 items per 8 domains) and is measured on a 1-7 scale where 1 indicates “To little or no extent” and 7 indicates “To a very great extent”. Users also have the option to choose N/A (Not able to answer), and are encouraged to do so if they are not familiar with that aspect of the program. The PSAT is directly linked to the eight domains outlined in the sustainability framework. Since this framework will be used to guide the action planning for each state, the scores from the PSAT will be important in assessing programmatic challenges and strengths related to sustainability. The sample for our survey is the workgroup defined by the program manager in each of the 24 participating states. We anticipate that 5-12 people in each state will complete the survey. PSAT scores are aggregated across participants for each state so that each state will have an overall PSAT score. Power calculations indicate that surveying workgroups in 24 states (12 intervention, 12 comparison) at three time points- intervention states at baseline and 12 and 24 months post training and comparison states at baseline and 12 and 24 months after baseline collection- will sufficiently capture group differences (Figure 4).

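### Section 4.0 has the study team help name the PSAT raters after states are allocated, and nothing conceals the arm from those staff

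*Combined protocol and SAP*

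**What the plan says.** Section 3.0 recruits 24 states and assigns them at random to two arms of 12. Section 4.0 then puts the naming of raters after that step: "Once we divide states into intervention or comparison group, we will work with each state program manager to identify a sustainability workgroup". The same section says that workgroup composition is not randomized.

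The workgroup is the PSAT sample. Section 5.1 (Phase 2, PSAT) states: "The sample for our survey is the workgroup defined by the program manager in each of the 24 participating states". It expects 5 to 12 people per state to complete the survey and combines their answers into one state score.

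Masking is described for the states only. Section 3.0: "States agreeing to participate in the study will learn of their group assignment after completing the PSAT". The comparison state protocol in Section 5.1 gives this as the reason for an identical webinar in both arms: "because state programs will be informed of their group selection after completing the PSAT".

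Section 5.1 times the roster differently by arm. In the intervention protocol: "Approximately two months before scheduled workshop, we will work with the state tobacco control program manager to identify the list of TC stakeholders". In the comparison protocol: "Before taking the PSAT, we will work with the state tobacco control program manager to identify the list of TC stakeholders". Both cite the same standardized selection criteria.

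**The concern.** Randomization makes the two sets of states comparable. It does not do the same for raters who are named later with advice from staff who may know the arm. In this trial the raters are the measuring instrument: they produce the PSAT outcome and also the baseline PSAT covariate in Equation 1 (Section 9.0). If advice on whom to include leaned one way in one arm, even slightly and without intent, part of any PSAT difference between arms could reflect who answered and not what the training did.

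The protocol itself treats composition as important. Section 4.0 says that the desired organizational outcome is best reached with a mixed group of internal staff, external stakeholders and policy makers. Several PSAT items (champions, leadership support, existence of a sustainability plan) are ones on which insiders and outsiders could plausibly differ.

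**Working it through.** The plan gives no figure for rater selection, so there is no stated value to reproduce. The check is of the sequence first, then of how much one rater can weigh.

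**1. Sequence.** Sections 3.0, 4.0 and 5.1 can be read as one order: states allocated; roster named by the manager with the study team; webinar; baseline PSAT; states told their arm; workshop in intervention states. The roster therefore falls after allocation and before the states are unmasked.

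**2. Who is masked at the roster step.**
- State programs, including the manager: yes, until the PSAT is completed (Sections 3.0 and 5.1).
- Study staff who work with the manager: no provision in any section.

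**3. Timing anchor.** The intervention roster is timed back from a workshop. Comparison states receive no further training component until year four, so during the trial only intervention states have that anchor. This fits poorly with states not knowing their arm until after the PSAT. The comparison anchor, ahead of the PSAT, would serve both arms.

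**4. Weight of one rater.** Inputs: 5 to 12 completers per state (Section 5.1) and 12 states per arm (Sections 5.1 and 9.0). Equal weighting and a one-point difference on the 1-7 scale are assumptions.
- Weight = 1/n: 1/12 = 0.083 and 1/5 = 0.200, or 8% to 20% of one state's score.
- Shift in that state's mean = 1 × weight = 0.08 to 0.20 points.
- Shift in the arm mean if this happens in one state = weight/12: 0.083/12 = 0.007 and 0.200/12 = 0.017 points.
- Shift in the arm mean if it happens in k states, all in the same direction = (k/12) × weight. For k = 6 this is 0.04 to 0.10. For k = 12 it is 0.08 to 0.20.

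**5. Baseline adjustment.** If the differing rater is off by the same amount at every time point, a baseline slope b leaves (1 − b) of the shift. With b assumed between 0.9 and 0.5, one state keeps 0.083 × 0.1 = 0.008 to 0.200 × 0.5 = 0.100 points. Adjustment does not remove a difference between raters whose scores would change differently over time.

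**6. Limit.** The documents give no SD for the PSAT and no evidence on how roster advice shifts scores. These points therefore cannot be turned into a bias estimate or set against the effect size of 1.25 in Section 9.0.

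**The case against.** The strongest reply is that the person who defines the workgroup is masked. Sections 5.1 and 10.0 describe the members as the program manager's choice, and the manager does not learn the arm until the PSAT is done. Both arms use the same standardized criteria. Equation 1 adjusts for baseline PSAT, and Section 5.1 checks PSAT answers against program records and the manager interview.

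Much of this stands, and it limits the risk. It does not close the gap. Sections 4.0 and 5.1 have the study team working with the manager on the list, so staff take part. The content of the criteria is in a cited source, so the discretion they leave cannot be judged here. Baseline adjustment handles mainly a constant rater difference. The record and interview checks can show disagreement but do not prevent selection, and PSAT replies are anonymous and aggregated by state, which makes later correction by rater difficult.

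It is also fair to object that one rater's weight in one state is not an arm-level effect. That is right: 0.08 to 0.20 points becomes 0.007 to 0.017 on the arm mean unless selection runs the same way in many states, and nothing in the documents shows that it would.

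**Conclusion.** The concern holds as an avoidable design gap: the plan places rater selection after allocation, with input from staff from whom the arm is not concealed. With 24 randomized units and a simple remedy, the change should be made. The size of any bias is unknown. The weights above rest on equal weighting, 5 to 12 completers and an assumed one-point difference. The reading rests on the text, because the schema figure in Section 5.3 was not available.

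A reader might infer more than the documents support:
- *That managers or states choose raters knowing their arm.* Sections 3.0 and 5.1 say the opposite for the baseline PSAT.
- *That the workshop-based timing unmasks intervention states.* No section says that managers are told of a workshop date before the PSAT. The timing is a tension to reconcile, not a shown unmasking.
- *That the people who deliver training also pick raters.* Section 4.0 says "To register, participants email the research project manager identified in the letter", and Section 5.1 says "To ensure training fidelity, delivery of all training components will be overseen by" the principal investigator and a project manager. The documents do not say that the two project-manager references are one role. Receiving registration emails is also not the same as advising on rosters.
- *That the 86% response in earlier PSAT work raises one rater's weight.* Section 5.1 already counts the 5 to 12 as completers, so this would discount twice.
- *That only PSAT scores could be affected.* Section 4.0 links workgroup composition to institutionalization, so this is not established either.

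**What to change.** In Section 4.0, replace the clause that puts roster naming after division into arms. State that each state's roster is named and recorded under the standardized criteria before allocation is generated. If an allocation already exists, state that it is concealed from staff who advise on rosters until the roster is recorded.

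In Section 5.1 (Preparing for the workshop), time the roster step from the PSAT, as the comparison state protocol does. Both arms then share one anchor, and the wording agrees with the masking of states in Sections 3.0 and 5.1.

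The cost is wording and sequencing. Both arms already need a roster before the baseline PSAT, so no new data are collected and the sample size does not change. Allocation has to wait for the rosters, and workshops may be booked slightly later. The concealment option needs roster advice from staff who have not seen the allocation. The change covers the baseline roster only; it does not settle who responds at 12 and 24 months, when states know their arm.
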